^k For Cohort 1, the consent will be signed after completion of the final visit in prior ARQ-154 study. Cohort 2 will sign consent prior to any study-related procedures at the Screening Visit.

- ^l For Cohort 1, this data will be obtained from the final visit of the prior ARQ-154 Study and used as the Day 1 data for this long-term safety study (ARQ-154-214). If after the prior ARQ-154 study completion, subjects should complete the screening visit procedures. The Baseline values for Safety tabulations will be taken from the day that the subject received their first active IP (across prior ARQ-154 studies and ARQ-154-214). Baseline values for efficacy will be those recorded on Day 1 of the prior ARQ-154 Study. For Cohort 2, Baseline evaluations will be obtained for all procedures and the Baseline/Screening version of the C-SSRS will be utilized at Screening. For Cohort 2, Screening labs that are collected within 14 days of Day 1 do not need to be repeated.
- ^m For Cohort 2 adolescent subjects PK samples will be collected on Week 4 for adolescent subjects between 12 – 16 years old. Collect PK sample with the safety lab collection. Ensure PK will not be drawn on the area where investigational product is applied.
- ⁿ At select sites, the Investigator will collect samples for *Malassezia* testing on Cohort 1 Group 2 subjects at Weeks 4, 12, 24, 36, and 52. Samples will be collected from treated and untreated areas by swabbing the skin surface. Samples should be collected from the same areas as samples collected during the ARQ-154-116 Baseline visit.

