7.1.1. Baseline Definition

For subjects in Cohort 1, the baseline value for safety and efficacy parameters will be defined as the last observation prior to the first dose of ARQ-154 foam 0.3% in either the prior ARQ-154 study or this study (See [Section 7.2.1](#) for the definition of a treatment emergent event).

Additional analyses will be performed where the baseline value for subjects in Cohort 1 is defined as the last observation prior to the first dose of ARQ-154 foam 0.3% in this study. For the purpose of these latter analyses, study procedures will not be repeated; the information from the prior ARQ-154 study final visit will be carried over to the Day 1 visit for this study.

For subjects in Cohort 2, baseline values for efficacy and safety will be defined as the last observation prior to the first dose of ARQ-154 foam 0.3% in this study.

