6.1. Statistical Definitions and Algorithms

6.1.1. Baseline

There are three baseline definitions for the analyses:

- Primary baseline is defined as the last observation before the first dose of roflumilast foam 0.3% in either ARQ-154 parent study or this study for subjects administered vehicle previously.
- Open-label baseline (OLE baseline) is defined the last observation before the first dose of roflumilast foam 0.3% in this study. For subjects in Cohort 1 who choose to enroll in this study, study procedures will not be repeated; study sites will carry over the information from the prior ARQ-154 study to the Day 1 visit for this study. For subjects in Cohort 2 Group 4, the definition for Primary and OLE baseline is the same.
- Safety baseline is defined as primary baseline for Cohort 1 Group 1, and OLE baseline for Cohort 2 Group 3 and Group 4.

The following table described the baseline used in the analysis:

Cohort Groups	Prior therapy, medical history	Demog and Efficacy Analysis	Safety Analysis for AE, PHQ8, PHQ-A, Prior and Concomitant medications	Safety Analysis for lab, vital signs and tolerability assessments
Cohort 1 Group 1	OLE baseline	Primary baseline and OLE baseline	OLE baseline	Primary baseline
Cohort 2 Group 3	OLE baseline	Primary baseline and OLE baseline	OLE baseline	OLE baseline
Cohort 2 Group 4	OLE baseline	Primary baseline and OLE baseline	OLE baseline	OLE baseline
Cohort 2 Total	OLE baseline	Primary baseline and OLE baseline	OLE baseline	OLE baseline

Overall	OLE baseline	Primary baseline and OLE baseline	OLE baseline	Safety baseline of roflumilast foam 0.3% in this study for subjects in the safety analysis population. For subjects in Cohort 2 Group 4, the definition for Primary and OLE Baselines is the same
----------------	--------------	-----------------------------------	--------------	---

Baseline values will most commonly be from Day 1.

For subject tolerability assessments, baseline is derived as the last non-missing measurement taken on the day of first application of study drug.

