9.3. Clinical Laboratory Evaluations

Laboratory test results will be summarized descriptively by groups and study visit as both observed values, changes, and percent changes from baseline values for continuous hematology, chemistry, and urinalysis results. Categorical urinalysis results will be summarized using frequencies by groups and study visit.

The number of subjects with clinical laboratory values below, within, or above the normal range by study visit and in relation to baseline will be tabulated for each clinical laboratory analyte (shift table).

Primary baseline will be used for Cohort 1 Group 1 and OLE baseline for Cohort 2. Overall group will be summarized using Safety baseline.

Abnormal laboratory values will be presented in the listings.

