9.5. PHQ-8

PHQ-8 will be completed by adult subjects and modified PHQ-A will be completed by adolescent subjects of age 12-17 years inclusive. Data for PHQ-8 and Modified PHQ-A will be classified using each subject's total score at a time point into a category based on the following scoring system:

- None – Minimal depression (0 to 4)
- Mild depression (5 to 9)
- Moderate depression (10 to 14)
- Moderately severe depression (15 to 19)
- Severe depression (20 to 24)

Shift tables showing the category of severity at each study visit will be presented by group. As PHQ-A is not assessed in ARQ-154-203 study, only OLE baseline will be used for this summary.

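### The PHQ-8 shift table uses only the open-label baseline, for a reason that covers only the adolescent PHQ-A, and departs without disclosure from the protocol's Cohort 1 safety baseline

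*SAP*

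**What the plan says.** **Protocol.** Section 7.1.1 sets the Cohort 1 baseline, for safety as well as efficacy, at "the last observation prior to the first dose of ARQ-154 foam 0.3% in either the prior ARQ-154 study or this study". A baseline taken in this study is reserved for additional analyses. Footnote l to the schedule (section 1.3, repeated in SAP 3.7) agrees: "The Baseline values for Safety tabulations will be taken from the day that the subject received their first active IP". Section 7.2.4, on PHQ-8 and PHQ-A shifts, names no baseline of its own, so the general rule applies.

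**SAP.** Section 6.1.1 defines two time points:

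- "Primary baseline is defined as the last observation before the first dose of roflumilast foam 0.3% in either ARQ-154 parent study or this study"
- "Open-label baseline (OLE baseline) is defined the last observation before the first dose of roflumilast foam 0.3% in this study"

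The 6.1.1 table has a column headed "Safety Analysis for AE, PHQ8, PHQ-A, Prior and Concomitant medications", with the open-label (OLE) baseline in every row, including Cohort 1 Group 1. Section 9.5 assigns the instruments by age: "PHQ-8 will be completed by adult subjects and modified PHQ-A will be completed by adolescent subjects of age 12-17 years inclusive". It then gives its reason for the baseline: "As PHQ-A is not assessed in ARQ-154-203 study, only OLE baseline will be used for this summary". Section 9.6 gives the same reason for CDI-2.

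For laboratory data on the same Group 1 subjects, SAP 9.3 says: "Primary baseline will be used for Cohort 1 Group 1 and OLE baseline for Cohort 2". Sections 9.2 (tolerability) and 9.4 (vital signs) follow the same rule, and all three use Safety baseline for the Overall column. Section 10 lists five changes from the planned analysis. The PHQ baseline is not among them.

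**The concern.** The SAP keeps the analysis that the protocol calls additional and drops the main one, for a reason that does not apply to adults. Nothing in either document says that PHQ-8 was missing from ARQ-154-203.

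Mood is a stated safety interest. Protocol 3.3.2 reports psychiatric adverse events in 5.9% of patients on oral roflumilast and 3.3% on placebo, with depression among the commonest. Protocol 4.2.1 names PHQ-8 in its safety monitoring. For subjects already on drug at rollover, a shift measured from rollover describes change since Week 8 of treatment. It does not describe change since treatment began, which is what the protocol's definition would give and what a reader of the safety tables would expect beside the laboratory and vital-sign tables.

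**Working it through.** The plan gives no power, precision or PHQ event-rate figure for this table. The check therefore covers the time offset, the classification, and who is affected.

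**1. Drug exposure before the open-label baseline.** SAP Table 2 gives target days from primary baseline for former roflumilast subjects, and Table 3 gives them from OLE baseline. The offset is the Table 2 day minus the Table 3 day:

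- Week 4: 85 − 29 = 56
- Week 12: 141 − 85 = 56
- Week 24: 225 − 169 = 56
- Week 36: 309 − 253 = 56
- Week 52: 421 − 365 = 56

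This matches the SAP's own target day of 56 for ARQ-154-203 Week 8, and 56 / 7 = 8 weeks. The lower window bounds also differ by 56 at every visit (for example 71 − 15 and 366 − 310).

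**2. What each baseline shows.** The SAP 9.5 categories are 0–4 none/minimal, 5–9 mild, 10–14 moderate, 15–19 moderately severe and 20–24 severe. The score paths below are illustrative:

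| Pre-dose / rollover / later | From primary baseline | From OLE baseline |
|---|---|---|
| 2 / 8 / 8 | none to mild (+1) | mild to mild (0) |
| 3 / 8 / 12 | none to moderate (+2) | mild to moderate (+1) |
| 8 / 3 / 3 | mild to none (−1) | none to none (0) |
| 8 / 3 / 8 | mild to mild (0) | none to mild (+1) |

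The first two rows hide or understate worsening. The third hides improvement. The fourth reports worsening that is only a return to the pre-dose level.

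**3. Size, under assumption only.** The documents give no rate. Suppose that a share q of the affected subjects changes category by Week 8, and a separate 3% worsens later. Take q as 1%, 3%, 5% or 10%.

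- If q is persistent worsening, the primary-baseline table shows q + 3% worsened = 4%, 6%, 8% or 13%, and the OLE table shows 3% each time.
- If q is improvement followed by return to the pre-dose category, the two reverse: primary baseline shows 3%, and OLE shows 4%, 6%, 8% or 13%.

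**4. Who is affected.** SAP section 8 says the two baselines coincide for former vehicle and de novo subjects. For Cohort 2, which includes the Group 3 rollovers with a gap, Protocol 7.1.1 itself sets the baseline in this study. That leaves adults in Cohort 1 Group 1 who received roflumilast in ARQ-154-203. The documents do not give their number.

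**5. Is there a pre-dose PHQ-8?** SAP 9.5 and 9.6 name only PHQ-A and CDI-2 as not assessed in ARQ-154-203, which implies that PHQ-8 was. Protocol 6.1 (Day 1 Visit) takes Cohort 1 Day 1 values for all three instruments from the prior study's final visit. That conflicts with SAP 9.5–9.6 for two of the three, and it concerns the last visit, not a pre-dose one. It is weak support.

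**6. A related conflict.** SAP 6.1.1 says Cohort 1 procedures are not repeated at Day 1 and values are carried over. If ARQ-154-203 had no PHQ-A or CDI-2, Group 1 has nothing to carry over, and the OLE baseline that SAP 9.5–9.6 prescribe may not exist for its minors.

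**The case against.** The OLE baseline can be defended as a consistent choice. The 6.1.1 table groups PHQ with adverse events and medications, SAP 9.7 uses OLE baseline for C-SSRS, and the protocol provides for a this-study baseline. The 8 parent-study weeks also had a vehicle arm, so an uncontrolled extension table is not the natural place to judge them. These points support keeping the OLE table. They do not explain dropping the other one: Protocol 7.2.1 anchors treatment-emergent events to this study expressly, whereas section 7.2.4 makes no such exception for PHQ.

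A reader might infer that the table is biased toward no shift. The documents do not support that. Under path 8 / 3 / 8 the OLE baseline shows more worsening, and nothing says how scores moved in ARQ-154-203.

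A reader might also take the 5.9% and 3.3% figures as an expected effect. They concern oral tablets and all psychiatric events, including insomnia, and say nothing about the size of a PHQ-8 change on foam.

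Hidden worsening may also be limited in severity. Protocol 6.1.4 appears to apply a Day 1 exclusion of PHQ-8 above 10 to everyone, while exclusion criterion 16 sits under Cohort 2 only. If the 6.1.4 limit applies to Cohort 1, no one enters with a score above 10, so a change hidden at rollover ends at mild, or at moderate with a score of exactly 10. No choice of baseline recovers subjects who do not roll over.

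The objection that stands in full is that a pre-dose PHQ-8 is inferred, not stated.

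**Conclusion.** The point holds as an unexplained departure of the SAP from the protocol for one descriptive safety table. The reason given does not cover PHQ-8, the departure is not listed in SAP section 10, and it is out of line with laboratory data, vital signs and tolerability for the same subjects. The consequence is confined to former roflumilast adults in Cohort 1 Group 1, whose category changes over 8 weeks are lost if still present at rollover. The direction is not fixed and the size cannot be computed; the percentages in the working are assumptions. No hypothesis test is affected, because the study has none. The remedy rests on a pre-dose PHQ-8 having been collected in ARQ-154-203. If it was not, the analysis may stay as it is, but the stated reason is still wrong for adults and needs replacing.

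**What to change.** 1. Add a PHQ-8 shift table from primary baseline for Cohort 1 Group 1, with Safety baseline for the Overall column, as in SAP 9.2–9.4.
2. Keep the OLE-baseline PHQ-8 table and label it as the additional analysis of Protocol 7.1.1.
3. Correct the PHQ8 entry in the 6.1.1 table, and limit the sentence on ARQ-154-203 in SAP 9.5 to PHQ-A.
4. First confirm whether ARQ-154-203 collected PHQ-8 before dosing. If it did not, give that as the reason in 9.5 and list the departure in SAP section 10.
5. Reconcile Protocol 6.1 and SAP 6.1.1 with SAP 9.5–9.6 on whether Cohort 1 Group 1 has any carried-over Day 1 value for PHQ-A or CDI-2, and state which baseline those summaries use if it does not.

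The cost is SAP wording and one descriptive table, with no new data collection. Parent-study values are already needed for the laboratory and vital-sign tables. Whether the PHQ-8 data are in the same transfer has to be checked.

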9.6. CDI-2

Parents/caregivers will complete the CDI-2 for subjects belonging to 9-11 years of age inclusive. For CDI-2, descriptive summaries of observed values, changes and percent changes from baseline will be calculated for the total score and the 2 scales emotional problems and functional problems by groups and study visit.

As CDI-2 is not assessed in ARQ-154-203 study, only OLE baseline will be used for this summary.

9.7. C-SSRS

The C-SSRS is a questionnaire that prospectively assesses Suicidal Ideation and Suicidal Behavior. At the Screening study visit, “Baseline/Screening” version of the C-SSRS will be used for Cohort 2 only; otherwise, the “Since Last Visit” version of the C-SSRS will be used. This version assesses Suicidal Ideation and Suicidal Behavior during the subject's lifetime and during the past 6 months. For the Screening visit, “lifetime” experience of the subject with Suicidal Ideation and Suicidal Behavior will be summarized. From Baseline visit, the “Since Last Visit” version will be used.

Suicidality data collected on the C-SSRS with positive responses will be listed for all subjects if there is any. Tables will include results from the Suicidal Ideation and Suicidal Behavior sections of the C-SSRS. Frequencies and percentages of subjects with a response of “Yes” at any point on

the Suicidal Ideation and Suicidal Behavior items will be summarized by study visit. OLE baseline will be used for this summary.

9.8. Physical Examination

The number and percentage of subjects with normal and abnormal findings in the physical examination will be displayed at each study visit by group for OLE data only.

9.9. Pigmentation Assessment

The hypopigmentation and hyperpigmentation are scored on a 0-3 scale where 0 = none, 1 = mild, 2 = moderate and 3 = severe. A shift table summarizing each category and study visit will be summarized for subjects belonging to Cohort 2 Group 4 for OLE baseline. This summary is repeated for race subgroups as well (white, black, vs others).

10. Changes from Planned Analysis

Per the sponsor request, the following changes have made to the SAP:

- The 2-grade improvement in IGA from Baseline as observed over time endpoint has been removed.
- TEAE by PT, TESAE by SOC, PT table summaries have been added.
- Shift in pigmentation assessment summary for Cohort 2 Group 4 is added.
- Subgroup analysis tables for TEAE by severity have been added.
- The Durations of IGA Success, Duration of IGA 0/1 and other similar duration variables have been updated to be defined from first instance of the event to first subsequent instance of loss of the event, rather than the time from the first instance of the event to the last subsequent instance of the event.

11. Other Planned Analysis

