^c IGA will be a 5-point scale ranging from completely clear (0) to severe (4). IGA should be completed prior to other physician assessments. Overall assessment of erythema (0-3 scale) and overall assessment of scaling (0-3 scale) will be completed. Total BSA affected by seborrheic dermatitis will be determined at each visit. A body diagram should be used to record areas of seborrheic dermatitis involvement.

^d Adolescents and adults will complete the C-SSRS (12 years of age and older). Adults will complete the PHQ-8. Adolescents (ages 12 -17, inclusive) will complete the modified PHQ-A. Parents/caregivers will complete CDI-2 (parent report) for children 9-11 years of age, inclusive.

^e A pregnancy test will be administered to all females of child-bearing potential. A serum pregnancy test will be performed at the Screening visit only for Cohort 2. A urine pregnancy test will be performed at Day 1, Weeks 4, 12, 24, 36 and 52. A negative result is required for continued participation in the study, and results must be available prior to dispensing of IP at each visit.

^f Local tolerability will be assessed prior to IP application in the clinic for the Investigator assessment of skin (Berger and Bowman skin irritation score) and 10-15 minutes post IP application for the subject's '0-3' burning/stinging assessment at Baseline. Note for Investigator tolerability assessments: **reactions at the site of product application, which may occur post-Baseline, should be differentiated from the preexisting inflammation associated with the subject's seborrheic dermatitis.** At Weeks 4, 12, 24, 36, and 52 will be a recall assessment of burning/stinging experienced post drug application on the previous day of the clinic visit.

^g An assessment for hypopigmentation and hyperpigmentation will be performed by the investigator at all clinic visits.

^h At selected sites, medical photography will be obtained for target lesions. All efforts will be made to de-identify the subjects. Subjects who are unwilling to participate in the medical photography will be allowed to opt out of this procedure.

ⁱ Kits will be dispensed based on %BSA affected. See IP Handling Manual for details.

^j Any emergent AEs will be followed in the clinic for up to one month at the Investigator's discretion until resolved or otherwise judged as clinically stable.

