6.1.9. Pigmentation Assessment

The Investigator will assess for pigmentation in areas affected previously and/or currently by seborrheic dermatitis at the timepoints outlined in the Schedule of Visits and Assessments ([Section 1.3](#)).

Hypopigmentation and hyperpigmentation will be scored individually using a 0 – 3 scale: ‘0’ for none, ‘1’ for mild, ‘2’ for moderate, and ‘3’ for severe.

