7.2. Safety Evaluation

Descriptive statistics will be calculated for safety data and presented by scheduled study visit for quantitative safety data and frequency counts will be compiled for classification of qualitative safety data. Summaries of local tolerability will be presented by scheduled study visit.

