3.1. Overall Design

This is an open-label, single-arm, long-term 52-week safety study of subjects with seborrheic dermatitis. This study will include both male and female subjects 9 years and older. Subjects rolling over from ARQ-154-116 (Cohort 1 Group 2) will not be summarized in the tables and would be listed only.

Cohort 1: This includes subjects of age 9 years or older from ARQ-154-203 and ARQ-154-116 studies and rolled into this extension study on the final visit from previous study. Subjects rolling over from ARQ-154-203 and ARQ-154-116 are separated into groups as indicated below.

Group 1: Subjects rolled over from ARQ-154-203 without gap

Group 2: Subjects rolled over from ARQ-154-116 (listings only and will not appear in summary tables)

Cohort 2: This includes subjects of age 12 years or older who may or may not have participated in a prior ARQ-154 study. The subjects could be either de novo subjects (requiring an IGA of disease severity of at least Moderate [“3”] at Baseline) or subjects who completed an ARQ-154 study before the initiation of this study (any IGA at Day 1 of this

study is allowed). Subjects in Cohort 2 are separated into groups as indicated below:

Group 3: Subjects rolled over from ARQ-154-203 with gap

Group 4: De novo subjects

Subjects will apply study drug once a day for up to 52 weeks. Subjects in both Cohorts cannot have more than 20% BSA affected by disease. All lesions on a subject will be treated including the scalp, face, trunk, and intertriginous areas.

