6.1.8. Data Adjustments/Handling/Conventions

All collected data will be presented in Clinical Data Interchange Standards Consortium (CDISC) datasets. Data not subject to analysis according to this plan will not appear in any tables or graphs but will be included only in the CDISC datasets.

All *P* values will be displayed in four decimals and rounded using standard scientific notation (eg, 0.XXXX). If a *P* value less than 0.0001 occurs it will be shown in tables as <0.0001; similarly, if a *P* value greater than 0.9999 occurs it will be shown in tables as >0.9999.

Adverse events will be coded using the MedDRA version 24.1 thesaurus. Medications will be coded using the World Health Organization Drug Dictionary Enhanced (WHO-DDE) Global B3 version September 2021.

A treatment-related AE is any AE with a relationship to the study drug of possibly related, probably related, likely related, or missing.

For partial AE and medication start dates:

- If the year is unknown, then do not impute the date but assign a missing value.
- If the year is known, but the month or month and day is unknown, then:
 - If the year matches the year of first dose date and the end date (if present) is after first dose date, then impute as the month and day of the first dose date.
 - Otherwise, assign 01 January.
- If the year and month are known, but the day is unknown, then:
 - If the month and year match the month and year of the first dose date, then impute as the day of the first dose date.
 - Otherwise, assign 01.

For partial AE and medication end dates:

- If the year is unknown, then do not impute the date but assign as missing value.
- If the year is known, but the month or month and day is unknown, then:
 - If the year matches the year of the last date of the study (date of last contact if subject lost to follow-up; date of completion or early termination otherwise), then impute as the month and day of the last date of the study.
 - Otherwise, assign 31 December.
- If the year and month are known, but the day is unknown, then:
 - If the month and year match the month and year of the last date of the study, then impute as the day of the last date of the study.
 - Otherwise, assign the last day of the month.

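### SAP 9.9 tabulates the hypo- and hyperpigmentation scores for de novo subjects only, without a stated reason, so the scores of ARQ-154-203 rollovers reach no planned table

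*SAP*

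**What the plan says.** **Collection.** Footnote g of the schedule (Protocol 1.3, repeated in SAP 3.7) reads: "An assessment for hypopigmentation and hyperpigmentation will be performed by the investigator at all clinic visits". Protocol 6.1.9, which sits under Safety Assessments, says: "The Investigator will assess for pigmentation in areas affected previously and/or currently by seborrheic dermatitis at the timepoints" in the schedule, and "Hypopigmentation and hyperpigmentation will be scored individually using a 0 – 3 scale". None of these places limits the assessment to a cohort or group.

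**Analysis.** SAP 9.9 says: "A shift table summarizing each category and study visit will be summarized for subjects belonging to Cohort 2 Group 4 for OLE baseline". The same summary is repeated by race (white, black, other). SAP 10, which lists changes from the planned analysis, confirms the scope: "Shift in pigmentation assessment summary for Cohort 2 Group 4 is added". SAP 3.1 defines the group: "Group 4: De novo subjects". The rollovers from ARQ-154-203 are Group 1 (no gap) and Group 3 (with a gap).

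**General rules.** SAP 6 sets the default columns for tables and figures: Group 1 and Group 3, each by prior roflumilast, vehicle and total, then Group 4, Cohort 2 Total and Overall. Protocol 7.2 says of safety data in general that "frequency counts will be compiled for classification of qualitative safety data". SAP 6.1.8 adds: "Data not subject to analysis according to this plan will not appear in any tables or graphs".

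**The concern.** This is a long-term safety study. A skin-safety score collected for up to 52 weeks in all subjects is to be tabulated in one group only. The omitted rollovers include the subjects with the longest roflumilast exposure, namely those who received active foam in ARQ-154-203. The breakdown by race is also drawn from Group 4 alone, so its cells are smaller than the collected data allow.

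The restriction is specific and stated twice (SAP 9.9 and SAP 10). It therefore overrides the default columns and cannot be read as loose drafting that those columns would repair.

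**Working it through.** The plan states no figure for this point, and SAP 3.2 says the sample size does not rest on power or precision. The check is therefore one of coverage.

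**1. Who is scored and who is tabulated**

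| Group | Scored at clinic visits | Pigmentation table |
|---|---|---|
| Cohort 1 Group 1 (203 rollover, no gap) | yes | none |
| Cohort 2 Group 3 (203 rollover, gap) | yes | none |
| Cohort 2 Group 4 (de novo) | yes | shift table and race repeat |
| Cohort 2 Total, Overall | n/a | none |

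Cohort 1 Group 2 (ARQ-154-116, about 10 subjects) is listings-only throughout the SAP by design and is not part of this point. The totals agree: about 400 + about 10 = about 410.

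**2. Does availability of a baseline explain the limit?**

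- Group 3 belongs to Cohort 2. The schedule marks pigmentation at Screening and Day 1, and footnote l says Cohort 2 baseline evaluations are obtained for all procedures. A shift from OLE baseline needs nothing from the parent study.
- Group 1 is uncertain. Footnote l carries its Day 1 data over from the final visit of the prior study. The same mark sits on the row for PHQ-8, PHQ-A and CDI-2, yet SAP 9.5 and 9.6 say PHQ-A and CDI-2 were not assessed in ARQ-154-203. The mark therefore does not show that a Day 1 pigmentation score exists.
- Without a Day 1 score, category frequencies at Weeks 4, 12, 24, 36 and 52 can still be tabulated.

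**3. How the SAP treats similar cases.** Where the parent study lacked an assessment (PHQ-A, CDI-2), the SAP gives that as the reason for its baseline choice and does not confine the tables to Group 4. For tolerability, laboratory values and vital signs (SAP 9.2 to 9.4) it handles different baselines across groups in one scheme. SAP 9.9 does neither.

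**4. Exposure.** The Week 52 OLE target is day 421 from primary baseline for prior-roflumilast rollovers (SAP Table 2) and day 365 for de novo subjects (SAP Table 3). The difference is 421 − 365 = 56 days, or 56 / 7 = 8 weeks. Vehicle rollovers have no extra exposure.

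**5. Number of subjects.** The split of the roughly 400 is not given. As an assumption only, rollover shares of 25%, 50% and 75% would leave 0.25 × 400 = 100, 0.50 × 400 = 200 or 0.75 × 400 = 300 subjects without tabulated scores.

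**6. Size of the change.** The SAP 6 layout has 3 + 3 + 1 + 1 + 1 = 9 columns. The present plan uses 1, so 8 are added to each table.

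**The case against.** The best defence is that de novo subjects are the one group certain to have a never-exposed baseline measured in this study. For prior-roflumilast rollovers, OLE baseline follows drug exposure, so a shift from it is not a change from untreated skin. SAP 8 does equate primary and OLE baseline for vehicle rollovers, but that defines a baseline in the efficacy section and does not show that pigmentation was measured. This is a fair reason to read rollover shifts with care and to footnote them. It is not a reason to omit Group 3, or to omit by-visit frequencies for Group 1.

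A reader might go further than the documents allow in five ways:

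- **That pigment changes in rollovers would be invisible in the report.** They would not. TEAEs are tabulated by groups and overall, and all AEs are listed (SAP 9.1). The physical examination covers skin and is shown as normal or abnormal by group (SAP 9.8). Protocol 7.2.3 captures clinically significant examination changes as AEs. These are coarser routes: post-baseline examinations fall only at Weeks 24 and 52, and Protocol 6.6.1 counts an application site reaction as an AE only if it needs intervention, suspension or discontinuation of the product. Whether a pigment change would be classed as such a reaction is not stated.
- **That a promised table was removed.** Protocol section 7 names no pigmentation summary, the endpoint lists omit it, and SAP 10 presents the Group 4 table as an addition.
- **That every Group 1 subject has a Day 1 score.** Step 2 of the check shows why this is not established.
- **That SAP 6.1.8 confines rollover scores to the datasets.** Pigmentation is subject to analysis under 9.9, and the documents hold no inventory of listings. A listing is neither promised nor ruled out.
- **That the loss can be sized by an upper confidence bound assuming zero events.** The group split is unknown, and zero events is unrealistic: Protocol 3.1 notes that the disease itself may bring pigmentary changes, and the IGA grade for complete clearance in SAP 8.2.1 permits them.

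**Conclusion.** The point holds for the scored assessment. The only planned table of pigmentation scores, and its repeat by race, exclude Groups 1 and 3, although their scores are scheduled at every clinic visit and no reason is given. This falls short of the general commitment in Protocol 7.2 and of the SAP's own default columns.

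It should be corrected, but its reach is modest. It concerns a supplementary descriptive safety table and touches neither primary endpoint (TEAEs, SAEs). The number of subjects affected cannot be stated from the documents, and the 100 to 300 above is arithmetic on assumed shares. The conclusion itself does not depend on those shares, nor on whether ARQ-154-203 scored pigmentation.

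**What to change.** In SAP 9.9, with a matching line in SAP 10:

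- Replace the restriction to Group 4 with the SAP 6 columns: Group 1 and Group 3 by prior roflumilast, vehicle and total; Group 4; Cohort 2 Total; Overall.
- Show shifts from OLE baseline for Groups 3 and 4, and for Group 1 subjects who have a Day 1 score.
- Where there is no Day 1 score, show the category frequencies at each visit without a shift.
- Footnote that OLE baseline follows drug exposure for prior-roflumilast subjects, so their shifts are not changes from untreated skin.
- Repeat by race on the same columns.

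The cost is extra columns in two planned tables. No new data are needed.
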